## 4. PARTICIPANT SELECTION

### 4.1 Pre-registration Eligibility Criteria

4.1.1 Females age  $\geq 18$  years

4.1.2 Post-menopausal defined as

- Age  $\geq 60$  and amenorrhea  $>12$  consecutive months  
OR
- Previous bilateral oophorectomy  
OR
- Age  $<60$  and amenorrhea  $>12$  consecutive months and documented follicle stimulating hormone (FSH) level within post-menopausal range according to institutional standard

NOTE: If FSH level not within post-menopausal range according to institutional standard, but there is other evidence of post-menopausal status, exceptions may be granted by the PI.

4.1.3 Histologic proof of metastatic or locally advanced, unresectable breast cancer

4.1.4 History of ER positive (+) ( $\geq 10\%$  of cells positive on H&E), HER2 negative (-) breast cancer disease, either as a

(1) History of primary, operable ER+/HER2- invasive breast cancer

OR

(2) History of *de novo* metastatic breast cancer that is ER+/HER2-

**Note: HER2- (negative) disease defined as one of the following:**

- HER2 IHC expression of 0, 1+ and ISH non-amplified
- HER2 IHC expression of 0, 1+ and ISH not done
- HER2 IHC expression of 2+ and ISH non-amplified
- IHC not done and ISH non-amplified

**Note: supporting documentation such as a pathology report from their primary diagnosis that indicates ER+/Her2- invasive breast cancer or a biopsy report of de novo metastatic breast cancer that is ER+/HER2- should be submitted through the RAVE database**

4.1.5 Prior treatment

- No more than two prior chemotherapy regimens in the metastatic setting.
- Prior treatment with fulvestrant in the metastatic setting is required, except for patients with a history of ER-negative metastatic breast cancer
- Unlimited prior endocrine therapy regimens in the metastatic setting are allowed

- No prior treatment with an Aurora Kinase inhibitor (either an Aurora A or pan-Aurora kinase inhibitor)
- 4.1.6 Disease that is measurable where:
- A non-nodal lesion is considered measurable if its longest diameter can be accurately measured as  $\geq 2.0$  cm with chest x-ray, or as  $\geq 1.0$  cm with CT scan, CT component of a PET/CT, or MRI.
  - A malignant lymph node is considered measurable if its short axis is  $\geq 1.5$  cm when assessed by CT scan (CT scan slice thickness recommended to be no greater than 5 mm).
- Note:** Tumor lesions in a previously irradiated area are not considered measurable disease.
- Note:** Disease that is measurable by physical examination only is not eligible.
- 4.1.7 No history of tumors involving spinal cord or heart.
- 4.1.8 Fully recovered from acute, reversible effects of prior therapy regardless of interval since last treatment
- EXCEPTION:** Neuropathies – if Grade 2 neuropathies have been stable for at least 3 months since completion of prior treatment, patient is eligible.
- 4.1.9a ECOG Performance Status: 0 or 1 (See [Appendix I](#))
- 4.1.9b No requirement for constant administration of proton pump inhibitor, H2 antagonist, or pancreatic enzymes (see [Appendix IV](#))
- 4.1.9c Willing to limit daily alcohol intake to the following: one 12-oz glass of beer, one 6-oz glass of wine, or one 1.5-oz portion of 80-proof alcohol.
- 4.1.9d No uncontrolled intercurrent illness including, but not limited to:
- ongoing or active infection
  - symptomatic congestive heart failure
  - unstable angina pectoris
  - uncontrolled symptomatic cardiac arrhythmia
  - uncontrolled hypertension (defined as blood pressure  $>160/90$ )
- 4.1.9e No history of uncontrolled sleep apnea syndrome and other conditions that could result in excessive daytime sleepiness, such as severe chronic obstructive pulmonary disease, or requirement for supplemental oxygen.
- 4.1.9f No other active second malignancy other than non-melanoma skin cancers and in situ cervical cancers within 5 years of registration.
- NOTE: A second malignancy is not considered active if all treatment for that malignancy is completed and the patient has been disease-free for at least 5 years prior to registration
- 4.1.9g Ability to provide written informed consent.

- 4.1.9h Willing to return to enrolling institution for follow-up during the active treatment. Event monitoring following completion of therapy may occur outside the enrolling institution.
- 4.1.9i No history of myocardial infarction  $\leq 6$  months prior to pre-registration or New York Heart Association (NYHA) Class III or IV heart failure (see [Appendix II](#)), uncontrolled angina, severe uncontrolled ventricular arrhythmias, or electrocardiographic evidence of acute ischemia or active conduction system abnormalities
- 4.1.9j No prior allogeneic bone marrow or organ transplantation
- 4.1.9k No known clinical finding or suspicion of human immunodeficiency virus (HIV) infection, hepatitis B, or hepatitis C.
- 4.1.9l No co-morbid systemic illnesses or other severe concurrent disease which, in the judgment of the investigator, would make the patient inappropriate for entry into this study or interfere significantly with the proper assessment of safety and toxicity of the prescribed regimens.
- 4.1.9m Able to swallow oral medication
- 4.1.9n No known GI disease or GI procedures that could interfere with the oral absorption or tolerance of alisertib. Examples include, but are not limited to partial gastrectomy, history of small intestine surgery, and celiac disease.
- 4.1.9o No visceral crisis: Visceral crisis is moderate-to-severe organ dysfunction as assessed by symptoms and signs, laboratory studies, and rapid progression of disease.
- 4.1.9p Willing to undergo a biopsy of a metastatic site of breast disease for central laboratory determination of ER and correlative research purposes. NOTE: If insufficient or no tissue is obtained by the pre-registration biopsy, an archival tissue specimen (preferably from a metastatic site) must be available to submit for Central Laboratory ER determination prior to registration.

## 4.2 Registration Eligibility Criteria

- 4.2.1  $\leq 28$  days post pre-registration
- 4.2.2 Central Laboratory ER determination completed.
- 4.2.3 The following laboratory values obtained  $\leq 14$  days prior to randomization:
- Absolute neutrophil count (ANC)  $\geq 1500/\text{mm}^3$
  - Platelet count  $\geq 100,000/\text{mm}^3$
  - Hemoglobin  $\geq 9.0$  g/dL
  - Total bilirubin  $\leq \text{ULN}$
- NOTE: If total bilirubin is out of range then direct bilirubin must be  $\leq \text{ULN}$

- Alanine transaminase (ALT)  $\leq 2.5 \times \text{ULN}$  ( $\leq 5 \times \text{ULN}$  for patients with liver involvement)
- Calculated creatinine clearance must be  $\geq 45$  ml/min using the Cockcroft-Gault formula below:

Cockcroft-Gault Equation:	
Creatinine clearance for females =	$\frac{(140 - \text{age})(\text{weight in kg})(0.85)}{(72)(\text{serum creatinine in mg/dL})}$

- 4.2.4 ECOG Performance Status: 0 or 1 (See [Appendix I](#))
- 4.2.5 Life expectancy of  $\geq 6$  months.
- 4.2.6 Willing to provide blood and tissue for correlative research purposes.

### 4.3 Registration Exclusion Criteria

- 4.3.1 Any of the following therapies prior to registration:
- Chemotherapy  $\leq 21$  days
  - Immunotherapy  $\leq 21$  days
  - Biologic therapy (includes monoclonal antibodies)  $\leq 21$  days
  - Hormonal therapy  $\leq 14$  days except fulvestrant  $\leq 21$  days
  - Targeted therapies including CDK 4/6 inhibitors (e.g. palbociclib, abemaciclib, ribociclib, etc.) and mTOR inhibitors (e.g. everolimus)  $\leq 21$  days
  - Other investigational agents  $\leq 21$  days
  - Radiation therapy  $\leq 14$  days
  - Minor surgical or interventional procedure  $\leq 7$  days
  - Major surgical procedure  $\leq 21$  days
- 4.3.2 Administration of myeloid growth factors or platelet transfusion  $\leq 14$  days prior to registration.
- 4.3.3 Systemic infection requiring IV antibiotic therapy  $\leq 14$  days prior to registration.
- 4.3.4 Treatment with clinically significant enzyme inducers, such as the enzyme-inducing antiepileptic drugs phenytoin, carbamazepine or phenobarbital, or rifampin, rifabutin, rifapentine or St. John's wort  $\leq 14$  days prior to registration.
- 4.3.5 Require constant administration of proton pump inhibitor, H2 antagonist, or pancreatic enzymes (see Appendix IV).
- 4.3.6 Development of visceral crisis since pre-registration.  
NOTE: Visceral crisis is moderate-to-severe organ dysfunction as assessed by symptoms and signs, laboratory studies, and rapid progression of disease.
- 4.3.7 History of brain metastases.

#### **4.4 Inclusion of Underrepresented Populations**

Individuals of all races and ethnic groups are eligible for this trial. There is no bias towards age or race in the clinical trial outlined. This trial is open to the accrual of women only.

## 5. REGISTRATION/RANDOMIZATION PROCEDURES

### 5.1 Pre-Registration (Step 0)

#### 5.1.1 TBCRC Institutions other than Mayo Clinic

To pre-register a patient, [REDACTED] a completed eligibility checklist to the [REDACTED] between 8 a.m. and 4:30 p.m. Central Time Monday through Friday.

#### 5.1.2 Mayo Clinic Institutions

To register a patient, access the [REDACTED] web page and enter the registration/randomization application. The registration/randomization application is available 24 hours a day, 7 days a week. Back up and/or system support contact information is available on the website. If unable to access the website, call the [REDACTED] [REDACTED] between the hours of 8 a.m. and 5:00 p.m. Central Time (Monday through Friday).

The instructions for the registration/randomization application are available on the [REDACTED] and detail the process for completing and confirming patient registration. Prior to initiation of protocol treatment, this process must be completed in its entirety and an MCCC subject ID number must be available as noted in the instructions. It is the responsibility of the individual and institution registering the patient to confirm the process has been successfully completed prior to release of the study agent. Patient registration via the registration/randomization application can be confirmed in any of the following ways:

- Contact the [REDACTED]. If the patient was fully registered, [REDACTED] staff can access the information from the centralized database and confirm the registration.
- Refer to “Instructions for Remote Registration” in section “Finding/Displaying Information about A Registered Subject.”

#### 5.1.3 Prior to accepting the pre-registration, the registration/randomization application will verify the following:

- IRB approval at the registering institution
- Patient pre-registration eligibility
- Existence of a signed consent form
- Existence of a signed authorization for use and disclosure of protected health information

#### 5.1.4 Pre-registration tests/procedures (see Section 11.0) must be completed within the guidelines specified on the test schedule.

## 5.2 Registration Procedures

### 5.2.1 TBCRC Institutions other than Mayo Clinic

#### 5.2.1.1 Registration

To register a patient, [REDACTED] a completed eligibility checklist to the [REDACTED] between 8 a.m. and 4:30 p.m. Central Time Monday through Friday.

#### 5.2.1.2 Correlative Research

A mandatory correlative research component requiring blood and tissue (see Section 9) is part of this study. The patient will be registered onto this component by the [REDACTED]

### 5.2.2 Mayo Clinic Institutions

#### 5.2.2.1 Registration

To register a patient, access the [REDACTED] web page and enter the registration/randomization application. The registration/randomization application is available 24 hours a day, 7 days a week. Back-up and/or system support contact information is available on the Web site. If unable to access the Web site, call the [REDACTED] [REDACTED] between the hours of 8 a.m. and 5:00 p.m. Central Time (Monday through Friday).

The instructions for the registration/randomization application are available on the [REDACTED] and detail the process for completing and confirming patient registration. Prior to initiation of protocol treatment, this process must be completed in its entirety and a MCCC subject ID number must be available as noted in the instructions. It is the responsibility of the individual and institution registering the patient to confirm the process has been successfully completed prior to release of the study agent. Patient registration via the registration/randomization application can be confirmed in any of the following ways:

- Contact the [REDACTED]. If the patient was fully registered, the MCCC Registration Office staff can access the information from the centralized database and confirm the registration.
- Refer to “Instructions for Remote Registration” in section “Finding/Displaying Information about A Registered Subject.”

#### 5.2.2.2 Correlative Research

A mandatory tissue and blood correlative research component is part of this study. The patient will be automatically registered onto this component (see Section 9).

### 5.2.3 All Institutions

5.2.3.1 Documentation of IRB approval must be on file in the [REDACTED] before an investigator may register any patients.

In addition to submitting initial IRB approval documents, ongoing IRB approval documentation must be on file (no less than annually) at the [REDACTED]. If the necessary documentation is not submitted in advance of attempting patient registration, the registration will not be accepted and the patient may not be enrolled in the protocol until the situation is resolved.

When the study has been permanently closed to patient enrollment, submission of annual IRB approvals to the Registration Office is no longer necessary.

5.2.3.2 Prior to accepting the registration, registration/randomization application will verify the following:

- IRB approval at the registering institution
- Patient eligibility
- Existence of a signed consent form
- Existence of a signed authorization for use and disclosure of protected health information

5.2.3.3 At the time of registration, the following will be recorded:

- Patient has/has not given permission to store and use his/her sample(s) for future research of cancer.
- Patient has/has not given permission to store and use his/her sample(s) for future research to learn, prevent, or treat other health problems.
- Patient has/has not given permission for someone to contact them about future participation in more research
- Patient has/has/not given permission to have coded genetic information and coded medical information placed in password protected, secured database for research analyses.

5.2.3.4 Treatment on this protocol must commence at a TBCRC institution under the supervision of a medical oncologist.

5.2.3.5 Treatment cannot begin prior to randomization and must begin  $\leq 7$  days after randomization.

5.2.3.6 Pretreatment tests/procedures (see Section 11) must be completed within the guidelines specified on the test schedule. Prior to registration/randomization a research biopsy of metastatic breast tissue must be taken for central pathologic review.

5.2.3.7 All required baseline symptoms must be documented and graded.

5.2.3.8 Study drug is available on site.

5.2.3.9 Blood draw kit is available on site.

### 5.3 Randomization Procedures

All institutions

- 5.3.1 The factors defined in Section 17.3, together with the registering membership, will be used as stratification factors.
- 5.3.2 After the patient has been registered into the study, the values of the stratification factors will be recorded, and the patient will be assigned to one of the following treatment groups using the Pocock and Simon dynamic allocation procedure which balances the marginal distributions of the stratification factors between the treatment groups.
- *Alisertib alone*
  - *Alisertib in combination with Fulvestrant*

### 5.4 Optional Crossover Phase

- 5.4.1 Patients in Arm 1 who meet the criteria in [Section 6.1.2](#) are eligible to crossover.
- 5.4.2 If the patient and physician want to cross over to Arm 2, [REDACTED] a completed continuation phase eligibility checklist to the Registration Office between 8 a.m. and 4:30 p.m. central time Monday through Friday.
- 5.4.3 Treatment cannot begin prior to registering to the crossover phase and will ideally begin  $\leq 7$  days after registration for the crossover phase.

## 6. TREATMENT PLAN

For both treatment arms:

- Study treatment by a local medical doctor (LMD) is not allowed. Routine and acute clinical care may be provided by LMD and reported to treating institution.
- If there is any interruption of treatment of  $\geq 21$  days contact Study Chair to determine whether the patient may restart treatment or will enter the event monitoring phase of the study.
- If hepatic panel on C1D1 indicates progressive liver involvement (increase in total bilirubin to  $>1.5$  x ULN or increase in ALT to  $>5$  x ULN), then patient is not allowed to start study treatment.  
Note to study staff: A comment should be added to the CRF stating that the patient had unacceptable liver enzyme levels on Cycle 1 Day 1 and did not start treatment.
- If CBC on C1D1 indicates new or worsening cytopenia(s), then starting dose of alisertib may be reduced based on discussion with overall study chair [REDACTED]
- Patients who have achieved complete response, partial response, or stable disease for  $\geq 2$  years may reduce imaging to every fourth cycle.

### 6.1 Arm 1 (Alisertib Monotherapy)

One treatment cycle=28 ( $\pm 3$ ) days

#### Alisertib Monotherapy Alone

Agent	Dose	Schedule	Route	Retreatment
Alisertib	50 mg BID*	Days 1-3, 8-10, 15-17	orally	every 28 ( $\pm 3$ ) days until disease progression

\*Doses should be taken 12 hours apart with a minimum of 6 hours in between

**Note: Cycle 1 Day15: The morning dose of alisertib should be taken prior to Cycle 1 Day15 blood draws**

- 6.1.1 Patients randomized to Arm 1 will initially receive alisertib until progression (PD) or intolerability.
- 6.1.2 At the time of progression on alisertib treatment, patients will be allowed to add fulvestrant to alisertib if all 3 of the following conditions (a thru c) are met:
  - a) Pre-registration biopsy finding of ER+ disease  
OR  
Pre-registration biopsy finding of ER  $<10\%$  positive or ER negative disease and a biopsy performed at the time of progression on alisertib demonstrates ER+  $\geq 10\%$  disease
  - b) Recovered from any non-hematologic toxicities to  $\leq$ Grade 1 and blood chemistries are such that

- Absolute neutrophil count (ANC)  $\geq 1500/\text{mm}^3$
- Platelet count  $\geq 100,000/\text{mm}^3$
- Hemoglobin  $>9.0 \text{ g/dL}$
- Total bilirubin  $\leq \text{ULN}$   
NOTE: If total bilirubin is out of range then direct bilirubin must be  $\leq \text{ULN}$
- Alanine transaminase (ALT)  $\leq 2.5 \times \text{ULN}$  ( $\leq 5 \times \text{ULN}$  for patients with liver involvement)
- Calculated creatinine clearance  $\geq 45 \text{ ml/min}$

c) Treatment with alisertib and fulvestrant must start at most 35 days after documentation of disease progression on alisertib alone

6.1.2.1 Patients who are not eligible or choose not to continue on with the combination of fulvestrant and alisertib will go to Event Monitoring (see Section 14.0).

### 6.1.3 Crossover Combination Therapy

One treatment cycle = 28 ( $\pm 3$ ) days

6.1.3.1 On the days both fulvestrant and alisertib are given, alisertib should be taken before fulvestrant is administered.

Agent	Dose	Schedule	Route	Retreatment
Fulvestrant	500 mg	Day 1 and Day 15 of 1 st crossover cycle; Day 1 of all subsequent cycles	intramuscular injection	every 28 ( $\pm 3$ ) days until disease progression
Alisertib	at dose level last used when given as a single agent*	Days 1-3, 8-10, 15-17	orally	

\* Doses should be taken 12 hours apart with a minimum of 6 hours in between

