## 7. EXPECTED TOXICITIES AND DOSING DELAYS/DOSE MODIFICATIONS

### 7.1 Dose Modification Based on Adverse Events

- 7.1.1 Dose modifications based on Adverse Event documented prior to each cycle of treatment. Strictly follow the modification in the table provided below until individual treatment tolerance can be ascertained. If multiple adverse events occur, administer the dose based on the greatest dose reduction required for any single adverse event observed. Dose modifications apply to the treatment given in the preceding cycle and are based on adverse events observed in the prior dose.
- 7.1.2 Note that fulvestrant administration is not modified for any adverse event.
- If alisertib is held due to toxicity then fulvestrant should also be held. Both agents should be restarted together.
  - If alisertib is discontinued due to intolerability then fulvestrant is also discontinued.
- 7.1.3 If treatment is held greater than 21 days without resolution of any adverse events other than severe neutropenia or a 3rd dose reduction is required then study treatment is to be discontinued\* and the patient will enter the Event Monitoring phase of the study.(see Section 14.0).  
\*Note: If patient is deriving benefit from study treatment and the event can be managed safely, consult Study Chair ([name]) regarding continuation.
- 7.1.4 Dose reduction levels

Dose Level	Alisertib (twice daily) Days 1-3, 8-10, 15-17
-1	40 mg
-2	30 mg

→ → Use the NCI Common Terminology Criteria for Adverse Events (CTCAE) version 4.0\* unless otherwise specified ← ←

\* Located at [REDACTED]

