Blood and lymphatic system disorders	
Febrile neutropenia
 
Grade 3 (neutrophils <1000 cells/mm^3 with a single temperature of >38.3°C (101°F) or a sustained temperature of ≥38°C (100.4°F) for more than one hour)
 
Grade 4 (Life threatening consequences)
	
Discontinue all study treatment*
 
*NOTE: If patient is deriving benefit from study treatment and event can be managed safely, consult Study Chair regarding continuation.

Gastrointestinal disorders	Mucositis oral Grade 3 or 4	
First event: Hold alisertib administration until recovered to ≤Grade 1 or pre-treatment level If recovered Grade 1 or baseline within 21 days, continue alisertib one dose level below current dose level
 
Second event: Hold alisertib administration until recovered to ≤Grade 1 or pre-treatment level If recovered to ≤Grade 1 or baseline within 21 days, continue alisertib one dose level below current dose level If not, discontinue all study treatment*
 
Third event: Discontinue all study treatment (see note*)
 
*NOTE: If patient is deriving benefit from study treatment and event can be managed safely, consult Study Chair regarding continuation.

Nervous system disorders	Somnolence ≥Grade 3	
Hold alisertib administration until recovered to ≤Grade 1 or pre-treatment level If recovered to ≤Grade 1 or baseline within 14 days, continue alisertib one dose level below current dose level If not, discontinue all study treatment (see note*)
 
NOTE: Evaluate whether patient alcohol consumption or utilization of benzodiazepines are contributing. If so, counsel patient to restrict alcohol and discontinue benzodiazepines with provider guidance.
 
*NOTE: If patient is deriving benefit from study treatment and event can be managed safely, consult Study Chair regarding continuation

Other unspecified adverse event reduction instructions	≥Grade 3	
Hold alisertib administration until recovered to ≤Grade 1 or pre-treatment level (baseline level) If recovered to ≤Grade 1 or baseline within 14 days, continue alisertib one dose level below current dose level If not, discontinue all study treatment *
 
*NOTE: If patient is deriving benefit from study treatment and event can be managed safely, consult Study Chair regarding continuation

### 7.3 Dose Modifications – Cycle 1 Day 15

The following dose modifications apply to adverse events documented on Cycle 1 Day 15 and the first crossover Cycle 1 Day 15.

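### After certain recovered toxicities in the last monotherapy cycle, Section 6.1.3 keeps the alisertib dose at crossover while Section 7.2 lowers it, and no text says which applies

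*Combined protocol and SAP*

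**What the plan says.** Section 6.1.2 governs entry to crossover: "patients will be allowed to add fulvestrant to alisertib if all 3 of the following conditions (a thru c) are met". Condition (a) concerns ER status. Condition (b) begins "Recovered from any non-hematologic toxicities to" Grade 1 or less and adds laboratory limits (ANC at least 1500, platelets at least 100,000, hemoglobin above 9.0, and liver and renal values). Condition (c) says that combination treatment "must start at most 35 days after documentation of disease progression on alisertib alone". None of the three mentions dose level or a stopping event under Section 7.

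The Section 6.1.3 table then gives crossover alisertib "at dose level last used when given as a single agent", with no exception for toxicity and no cross-reference.

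Section 7.1.1 introduces its rules as "Dose modifications based on Adverse Event documented prior to each cycle of treatment", and both it and Section 7.2 state: "Dose modifications apply to the treatment given in the preceding cycle and are based on adverse events observed in the prior dose". A typical Section 7.2 action, here from the somnolence row and the row for other events of Grade 3 or higher, is "If recovered to ≤Grade 1 or baseline within 14 days, continue alisertib one dose level below current dose level".

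Section 7.3 names crossover expressly: "The following dose modifications apply to adverse events documented on Cycle 1 Day 15 and the first crossover Cycle 1 Day 15". Section 7.2 does not mention crossover.

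Section 6.4.2 refers to Section 7 for a lower dose, but only for patients who have not progressed. Section 6.4.3 sends progressing Arm 1 patients to the Section 6.1 conditions.

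**The concern.** Take an Arm 1 patient who has a dose-reducing toxicity in the same cycle in which she progresses, and who then recovers. She passes the recovery test in Section 6.1.2. A site working from Section 6.1.3 restarts her at the level on which the toxicity arose, with a second drug added. A site working from Section 7.2 restarts her one level lower. Both can say that they followed the protocol.

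The first stake is starting-dose safety, in a trial that Section 3.8 says was closed temporarily after its safety boundary was crossed. The second is how to interpret objective 2.2.3 (response and median PFS during crossover treatment) and the separate crossover safety summary in Section 17.1.2.4. Both could pool patients whose starting dose was set under different rules.

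**Working it through.** No sample size, power or error rate is at issue. The check sets each row of the Section 7.2 table beside the 6.1.3 dose, for a patient whose event occurs in the last monotherapy cycle, who recovers within the time that Section 7.2 allows, and who meets Section 6.1.2.

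| Event in the last monotherapy cycle | Section 7.2 after recovery | Section 6.1.3 | Same dose? |
|---|---|---|---|
| Anemia, Grade 3 with Hb <7 or Grade 4, first or second episode | one level lower | last level | No |
| Grade 3 neutropenia, first episode, recovered at recheck #1 | same level | last level | Yes |
| Grade 3 neutropenia, first episode, recovered only at recheck #2 | one level lower | last level | No |
| Grade 3 neutropenia, second episode | one level lower | last level | No |
| Grade 4 neutropenia, first or second episode | one level lower | last level | No |
| Platelets Grade 1-2, recovered within 21 days | same level | last level | Yes |
| Platelets Grade 3, recovered at recheck #1 | same level | last level | Yes |
| Platelets Grade 3, recovered only at recheck #2 | one level lower | last level | No |
| Mucositis Grade 3-4, first or second event | one level lower | last level | No |
| Somnolence Grade 3 or higher | one level lower | last level | No |
| Other event of Grade 3 or higher | one level lower | last level | No |

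There is also no conflict when the reduction was already made in an earlier monotherapy cycle, because the last-used level is then the reduced one.

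**One patient followed through.** She is on 50 mg BID, has a first Grade 4 neutropenia in the cycle in which she progresses, and her ANC is at least 1500 at the first recheck. She meets the ANC limit in 6.1.2(b), and a recheck at 5 to 7 days can fall well inside the 35-day window. Section 6.1.3 gives 50 mg BID. Section 7.2 with the dose levels of Section 7.1.4 gives 40 mg BID. At a last dose of 40 mg the pair would be 40 and 30 mg. At 30 mg the next reduction would be the third (50 to 40, 40 to 30, then below 30), for which Section 7.1.3 prescribes discontinuation.

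**Events that end treatment.** Febrile neutropenia, Grade 4 platelets, Grade 3 platelets with bleeding, third episodes and failure to recover in time lead to discontinuation under Section 7.2. Section 7.1.3 adds a third reduction and sends the patient to event monitoring. Section 6.4.4 lists unacceptable adverse events as a reason to stop all protocol therapy, again followed by event monitoring. Most of these instructions carry an exception through the Study Chair. Section 6.1.2 does not repeat any of this among its three conditions.

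**Reach.** Section 17.2.1 anticipates 14 to 22 crossover patients, with a 95% binomial interval for response rate and for clinical benefit rate. One patient therefore carries 1/14 = 7.1 to 1/22 = 4.5 percentage points of either rate. The primary endpoint (Section 17.1.1) counts response during initial treatment only, so Arm 1 patients contribute nothing to it after crossover.

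**The case against.** The strongest reply is that Section 7 is an overlay on every dose table. Sections 7.1.1 and 7.2 act before each cycle, crossover is given in cycles, and neither section exempts it. The reductions take the preceding cycle's dose as their reference, and 6.1.3 supplies that reference. The Arm 1 and Arm 2 tables likewise state a flat 50 mg BID without pointing to Section 7, and nobody would say that they cancel it. Nor does the express mention of crossover in Section 7.3 prove that 7.2 excludes it: 7.3 concerns a single visit and needed the extension, whereas 7.2 covers all cycles.

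Much of this stands. The overlay is a plausible reading, and the contrast with 7.3 is weak evidence against it. But no sentence states the overlay, and other text pulls the other way:

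- Unlike the flat 50 mg tables, 6.1.3 is already written in dose levels, so a site can fairly take the level as settled there.
- Section 6.4.2 limits its pointer to Section 7 to patients without progression, and 6.4.3 directs progressing patients to Section 6.1.
- The study calendar for Arm 1 treats the start of the combination as a new Cycle 1, which leaves open whether the last monotherapy cycle counts as the preceding one.

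A reader might go further and infer that 6.1.3 orders treatment to restart in patients whom Section 7.2 takes off treatment. The documents do not support that. Crossover is only allowed, not required, and Sections 7.1.3, 7.2 and 6.4.4 already discontinue such patients or route them to event monitoring, subject to the Study Chair exception. What remains is that 6.1.2 does not list these events as a bar.

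**Conclusion.** The point holds for the reduction rows marked No in the table: read literally, Sections 6.1.3 and 7.2 give doses one level apart, and the documents do not say which governs. For stopping events the fault is an omission in 6.1.2, not an opposite order.

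The conflict requires a reduction-triggering event in the final monotherapy cycle, recovery, progression, and all three 6.1.2 conditions met. How many of the anticipated 14 to 22 crossover patients that describes cannot be derived from the documents. It is tempting to take the 5 of 12 patients in Section 3.8 (42%) as a guide, but that figure counts Grade 4 toxicity or death on treatment, and the text restricts it neither to Arm 1 nor to the last cycle before progression. That sites have in fact dosed differently is also not shown; crossover passes through a checklist at the Registration Office (Section 5.4.2), although nothing in the protocol says that it settles the dose.

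The consequence is confined to crossover safety and to crossover response, clinical benefit and PFS. The randomized comparison on the primary endpoint is untouched. The change should be made, because it concerns starting dose and costs almost nothing, but it does not threaten the trial's main conclusion.

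**What to change.** Reconcile Sections 6.1.2, 6.1.3, 6.4 and 7.1 to 7.2. Which rule governs is for the sponsor's clinical team; the sections need only agree.

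1. In the 6.1.3 table, state whether the first crossover dose of alisertib is subject to the Section 7.2 action for events in the last monotherapy cycle.
2. In Section 7.2, state its crossover scope explicitly, including whether the last monotherapy cycle is the preceding cycle for crossover Day 1. Bring the wording of 6.4.2 and 6.4.3 into line with it.
3. In Section 6.1.2, state whether a patient who met a discontinuation rule under 7.1.3, 7.2 or 6.4.4 may cross over, and whether the Study Chair exception applies to her.

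The cost is a few sentences in the next amendment and a matching line on the crossover checklist. No visits, procedures or patients are added, and no analysis changes.
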